5.7.2 Secondary endpoints

All secondary efficacy variables will be analyzed based on the FAS population.

For the analysis of continuous secondary efficacy variables, the ANCOVA model with change from baseline to respective time point as a response variable and respective baseline value and treatment group as the terms in the model will be used at each time point for the parameters listed below. The LOCF method will be used for missing data imputations.

- Changes in BNP and NTproBNP values after 12, 24 and 36 weeks of treatment
- Changes in inflammation markers (hsCRP, TNF- α , sUA, and plasma fibrinogen) after 12, 24 and 36 weeks of treatment
- Changes in oxidative stress parameters [Malondialdehyde (MDA), Myeloperoxidase (MPO) Oxidized low-density lipoprotein (Ox-LDL),] after 12, 24 and 36 weeks of treatment
- Changes in lipid profile after 12, 24 and 36 weeks of treatment
- Changes in eGFR with CKD-EPI formula after 12, 24 and 36 weeks of treatment
- Changes in urine albumin excretion as evaluated by first morning urine albumin/creatinine ratio (mg/g) after 12, 24 and 36 weeks of treatment
- Pulse Wave Analysis (including modifications of PWV, arterial stiffness, central blood pressure and augmentation index) after 12, 24 and 36 weeks of treatment
- The primary parameter PWV over time (12 to 36 weeks) will be analyzed using a repeated measurement model
- Changes in endothelial activation/adhesion markers (sVCAM, sICAM, vWF, e-selectine) after 12, 24 and 36 weeks of treatment (These parameters will be evaluated in a subset of patients enrolled in selected centers only)
- Tender and swollen joint count

Logistic regression will be used to analyze the parameters below for the difference between treatment groups at each time point where the dependent variable is defined as a binary outcome (e.g. 1 if urate concentration ≤ 6 mg/dl, 0 otherwise) and treatment group and baseline urate concentration will be included as independent variables.

- Percentage of gout patients with a serum urate concentration of less than or equal to 6 mg/dl after 12, 24 and 36 weeks of treatment
- Percentage of patients above the sUA target levels at Week 12, Week 24 and Week 36 after having reached the sUA target levels at Week 2

STATISTICAL ANALYSIS PLAN

Protocol No: MEIN/14/FEB-PWV/001 (FORWARD)

Version Number: 2.0

Date of Issue: 2018-03-16

Page 19 of 22

Proportional hazards model with treatment group as covariate will be used to investigate:

- Time to achieve sUA target levels for all patients with baseline sUA as additional covariate
- Time to achieve sUA target levels stratified for sUA levels at baseline as follows: 8.1-8.8 mg/dl, 8.9-9.6 mg/dl, 9.7-10.3 mg/dl, 10.4-11.0 mg/dl, >11 mg/dl
- Time to achieve sUA target levels for all patients and stratified for sUA levels at baseline as follows: >8 and <9 mg/dl, >9 and <10 mg/dl, ≥ 10 mg/dl will additionally be presented

In case of deviation from proportional Hazard-assumption the log-rank-test will be used instead.

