5.7.1 Primary endpoint

The primary efficacy endpoint is Pulse Wave Velocity (PWV) after 36 weeks of treatment with febuxostat or allopurinol.

At least two PWV measurements will be taken per visit. The evaluation of measurements will be performed by two independent laboratory teams. Values valid to be included in analysis will be selected by experienced medical experts. Details on processes related to the assessment and final selection of the PWV/PWA reports that will be used for the statistical analysis are described in the document named: “PWV/PWA reconciliation process” section 15.5 Appendix E of Data Management Plan. Mean values from all measurements considered to be valid will be calculated per visit and will result in one value per visit per parameter.

Analysis of covariance (ANCOVA) with the 36 weeks PWV value as dependent variable, treatment group as factor and age, baseline blood pressure, baseline PWV as covariates, will be used to compare the efficacy of the two treatment groups.

The assumptions of the underlying model such as normality of residuals and homogeneity of variance will be investigated using significance level of 0.1.

All covariates found not to be statistically significant at the 0.05 two-sided significance level, will be removed from the model and the final model will only include statistically significant covariates.

For covariates found to be significant, the treatment by covariate interaction will be evaluated using ANCOVA model with the terms for treatment, covariate and treatment by covariate interaction.

If interaction is statistically significant at the 0.1 two-sided significance level, additional analyses will be performed to explore the interaction.

A sensitivity analysis with the change from baseline to Week 36 as response variable will be performed similarly to the primary analysis.

The relationship between PWV at Week 36 (change from baseline to Week 36) and febuxostat as well as allopurinol dose will be explored using scatterplots.

The LOCF method will be utilized for missing data imputations as described in section 5.1.2.

STATISTICAL ANALYSIS PLAN

Protocol No: MEIN/14/FEB-PWV/001 (FORWARD)

Version Number: 2.0

Date of Issue: 2018-03-16

Page 18 of 22

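### PWV is modelled with age and baseline blood pressure in SAP 5.7.1 but without them in 5.7.2, so Week 36 PWV change may get two estimates and some precision may be lost

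*SAP*

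**What the plan says.** **Primary model (SAP 5.7.1).** Week 36 PWV is the response, with "treatment group as factor and age, baseline blood pressure, baseline PWV as covariates". A removal rule follows: "All covariates found not to be statistically significant at the 0.05 two-sided significance level, will be removed from the model". Age and blood pressure are therefore candidate covariates and not a fixed adjustment.

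**Week 36 change, first specification (SAP 5.7.1).** "A sensitivity analysis with the change from baseline to Week 36 as response variable will be performed similarly to the primary analysis". I read this as the same covariates, the same removal rule, the FAS and LOCF.

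**Week 36 change, second specification (SAP 5.7.2).** Continuous secondary variables are analysed as change from baseline, with the "respective baseline value and treatment group as the terms in the model will be used at each time point for the parameters listed below". The list that follows contains "Pulse Wave Analysis (including modifications of PWV, arterial stiffness, central blood pressure and augmentation index) after 12, 24 and 36 weeks of treatment", so PWV itself falls under this shorter model at all three visits. LOCF applies here too, and on the analysis set the section says: "All secondary efficacy variables will be analyzed based on the FAS population".

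**Repeated measures (SAP 5.7.2).** "The primary parameter PWV over time (12 to 36 weeks) will be analyzed using a repeated measurement model". No covariates are given.

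The SAP does not say why the PWV models differ, or which Week 36 change estimate is the one to cite.

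**The concern.** A short ANCOVA on own baseline is a normal common model for BNP, lipids or inflammation markers. PWV is different, because the SAP itself names age and baseline blood pressure as relevant to it and then leaves them out when the same variable is analysed again as a secondary endpoint.

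Two things are at stake, both modest:

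- **Two answers to one question.** Week 36 PWV change, in the same population with the same imputation, is assigned two ANCOVAs. If they differ, the report will carry two estimates and two p-values with no rule on which leads. The repeated-measures model could add a third.
- **Precision.** If age and blood pressure predict Week 36 PWV beyond baseline PWV, the secondary PWV analyses have wider intervals than they need.

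**Working it through.** **1. The plan's own figure.** Inputs from SAP 2.4: difference 1.8 m/sec, SD 3.75 m/sec, two-sided 0.05, power 85%, two-group t-test. The normal approximation gives 78 per arm. The exact noncentral t gives 84.6% power at 78 and 85.0% at 79, so the stated 79 per arm is reproduced. I use N = 2 × 79 = 158 below.

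**2. The response scale is not the source of any difference.** Let B be baseline PWV, T treatment and Z the other covariates. If Y36 = a + τT + βB + γZ + e, then Y36 − B = a + τT + (β − 1)B + γZ + e. The treatment effect τ and its standard error are identical. With baseline PWV in both models, a gap between the 5.7.1 and 5.7.2 estimates can only come from age and blood pressure.

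**3. Effect on the standard error.** Let R² be the share of the variance left after baseline PWV that age and blood pressure explain. The SAP gives no value, so I assume a range of 0 to 0.20. The short model has 158 − 3 = 155 residual degrees of freedom. With two more terms it has 153.

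SE factor (with / without) = √[(1 − R²) × 155/153]

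- R² = 0: √1.0131 = 1.007
- R² = 0.05: √(0.95 × 1.0131) = 0.981
- R² = 0.10: √(0.90 × 1.0131) = 0.955

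Break-even is at R² = 1 − 153/155 = 0.013. Below that, the two terms cost slightly more than they return.

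**4. How often the two Week 36 models coincide.** This was simulated with 4,000 trials per setting, N = 158 and SD 3.75. Assumptions: correlation of baseline with Week 36 PWV 0.6; age and blood pressure each correlated 0.4 with baseline PWV; true difference 0.9 m/sec. The expected SE of the short model is 3.75 × √(1 − 0.6²) × √(2/79) = 0.477, and the simulation gave 0.478. Removal was applied once, from the p-values of the full model.

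| Assumed R² | SE factor | Removal makes the models identical | SD of gap between estimates, no removal (m/sec) | Disagree on p < 0.05, no removal |
|---|---|---|---|---|
| 0 | 1.007 | 90% | 0.05 | 3% |
| 0.02 | 0.996 | 55% | 0.09 | 6% |
| 0.05 | 0.981 | 20% | 0.12 | 8% |
| 0.10 | 0.955 | 3% | 0.16 | 11% |
| 0.20 | 0.900 | <0.1% | 0.22 | 18% |

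The last two columns compare the full model, without removal, with the short one. They show how far apart the two specifications can lie, but they are not exact figures for the plan with its removal rule. The assumed true difference puts the expected test statistic at 0.9/0.478 = 1.88, close to the significance boundary, so the disagreement rates are near the high end.

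**The case against.** The strongest reply is that nothing here is invalid. Allocation is randomised 1:1, so ANCOVA on own baseline is unbiased, and chance imbalance is already reflected in its confidence interval. The confirmatory analysis is clearly designated as Week 36 PWV in the FAS (SAP 5.7 and 5.7.1), and both change analyses are supportive. One simple model for all continuous secondary endpoints is a defensible choice. All of this stands, and it limits the point to consistency and efficiency.

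A reader might infer more than the SAP supports, in four ways:

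- **That the Week 12 to Week 36 course mixes treatment change with model change.** It does not. SAP 5.7.2 uses one identical model at Weeks 12, 24 and 36, so a like-for-like series is already planned.
- **That two unequal Week 36 effects are certain.** They are not. If the removal rule drops age and blood pressure and keeps baseline PWV, the two models are the same.
- **That precision is necessarily lost.** This depends on an R² that the SAP does not give. Near zero, the added terms make the standard error slightly larger.
- **That arterial stiffness, central blood pressure and augmentation index lose precision too.** Nothing in the SAP shows this, since age and blood pressure are named only for PWV.

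It is also fair to say that fixing the covariates in 5.7.2 alone would not work. With removal still active in 5.7.1, that change could create a mismatch where the present models agree.

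**Conclusion.** The point holds as a minor one, for PWV only. SAP 5.7.1 and 5.7.2 assign different covariates to Week 36 PWV change in the same population, and the covariates of the repeated-measures PWV model are unstated. Whether the two Week 36 estimates differ is left to the outcome of a significance-based removal step. The possible loss of precision is about 2% of the standard error at a further 5% of variance explained, about 4.5% at 10%, and none near 0. These sizes rest on assumed R² values, on 158 evaluable patients and on blood pressure entering as one variable. The coincidence rates also rest on the assumed correlations. There is no bias, and the primary analysis keeps its standing.

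**What to change.** Use one pre-specified covariate set for PWV: age, one named baseline blood pressure measure and baseline PWV, all retained whatever their p-values. Apply it to the primary ANCOVA and its change-from-baseline version in SAP 5.7.1, to the PWV ANCOVAs at Weeks 12, 24 and 36 in 5.7.2, and to the repeated-measures PWV model. Delete the removal rule in 5.7.1, and name the blood pressure measure, because that section does not say whether systolic or diastolic is meant. The other PWA parameters can keep their present model.

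**Cost.** A few sentences in the SAP, made before database lock and unblinding as SAP 3.1 requires. No new data are needed, since the flow chart has demography at screening and blood pressure at screening and Day 0. The statistical cost is about two degrees of freedom, roughly 0.7% of the standard error if the covariates carry no information. If both systolic and diastolic pressure were entered, it would be √(155/152) = 1.010, about 1%.

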2.3 Study design

This study is designed as a randomized, active-controlled, open label, evaluator blind, parallel group, multi-center, multi-national, Phase IV trial. Patients will be randomized 1:1 to receive febuxostat or allopurinol.

There will be approx. 35 sites in the following countries: Germany, the Netherlands, Italy, Poland, Serbia, Romania.

Study duration for individual patients will be 39 weeks. This includes a one-week run-in/screening period which can be extended to max 30 days in case of re-testing, followed by a 36 weeks treatment and a 2 weeks safety follow-up (by phone call).

The study physician responsible for randomization and drug supply handling is unblinded to study medications and therefore will not be involved in the main efficacy evaluations of each patient randomized in the study.

Conversely, the study physician/s responsible for the main efficacy evaluation (Pulse Wave Velocity) will be blind to study treatments. In addition, key efficacy variables will be performed by an independent core laboratory where the central reader will be blind to the treatment assigned to patients.

Fasting lipid levels, NTproBNP, BNP, markers of inflammation and endothelial activation/adhesion, oxidative stress parameters, eGFR, changes in urine albumin excretion as evaluated by first morning albumin/creatinine ratio will be also measured by a central laboratory.

Eligible patients will be randomized to treatment with allopurinol 100 mg or febuxostat 80 mg (1:1 ratio). Up-titration of allopurinol or febuxostat to the maximum dose permitted in the study may be performed between Week 2 and Week 10, see flow chart below for details.

A follow-up safety assessment will be performed by a phone call 2 weeks after study termination.

STATISTICAL ANALYSIS PLAN

[figure not shown]
Protocol No: MEIN/14/FEB-PWV/001 (FORWARD)

Version Number: 2.0

Date of Issue: 2018-03-16

Page 10 of 22

Trial flow chart

Notes:

	Day -30 to Week -1	Day 0	Week 2 ± 4 days	Week 12 ± 4 days	Week 24 ± 4 days	Week 36 ± 4 days	Week 38 + 3 days after
	Visit -1	Visit 0	Visit 1	Visit 2	Visit 3	Visit 4	Visit 5 Phone call
	Screening	Randomization	On Treatment Visit	On Treatment Visit	On Treatment Visit	End of Study visit	Safety Follow up
Inclusion/exclusion crit.	X						
Informed consent	X						
Randomization		X					
Medical history	X						
Concomitant medications	X	X	X	X	X	X	
Physical examination	X			X	X	X	
Vital signs (BP, HR body temperature)	X	X		X	X	X	

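### The between-arm test of being above the sUA target after reaching it at Week 2 conditions on a post-randomization response and leaves its denominator open, so it is not a randomized comparison

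*SAP*

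**What the plan says.** SAP section 5.7.2 lists two binary urate outcomes under one rule: "Logistic regression will be used to analyze the parameters below for the difference between treatment groups at each time point". The model is fixed in the same sentence: "treatment group and baseline urate concentration will be included as independent variables". The first outcome is the proportion at or below 6 mg/dl at Weeks 12, 24 and 36. The second is this percentage: "patients above the sUA target levels at Week 12, Week 24 and Week 36 after having reached the sUA target levels at Week 2". Section 5 makes every test two-sided at 0.05 unless stated otherwise, and nothing marks the second item as descriptive.

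On the population, section 5.7.2 says only: "All secondary efficacy variables will be analyzed based on the FAS population". It does not say what happens to FAS patients who were not at target at Week 2.

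Section 2.3 starts patients on allopurinol 100 mg or febuxostat 80 mg and adds: "Up-titration of allopurinol or febuxostat to the maximum dose permitted in the study may be performed between Week 2 and Week 10". The flow chart shows Week 2 as the first on-treatment urate measurement.

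**The concern.** Randomization makes the arms comparable at baseline. It does not make Week-2 responders comparable, because Week-2 status is an outcome of treatment. If one starting regimen brings fewer patients to target by Week 2, those who do reach it are a more selected group: lower baseline urate, or a stronger response for reasons that are not measured. Baseline urate is in the model; unmeasured responsiveness is not. The more selected group will then tend to stay at target more often, even if the drugs control urate equally well from Week 12 on.

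At stake is how one secondary result is read. An odds ratio from this model would look like a treatment effect on loss of control. It could instead reflect which arm had more early responders.

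**Working it through.** **1. What the SAP supplies.** It states no expected rate or power for this item, so there is no figure to reproduce for it. The trial size is taken from section 2.4. There, 79 per arm gives 85.0% power for 1.8 m/sec with SD 3.75, as stated, and 79 × 1.15 = 90.85, hence 91 per arm. Allocation is 1:1, the model terms are treatment and baseline urate, and alpha is 0.05 two-sided.

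**2. What has to be assumed.** Week-2 response (febuxostat/allopurinol) of 50/50, 50/30, 70/30, 70/10 and 80/5%. Late status (above target) of 30% in both arms with no treatment effect, so the true odds ratio is 1. An unmeasured responsiveness factor with SD 1 that acts on both Week-2 and late status, with log-odds coefficient g from 0 to 2. Each scenario used 1,000,000 simulated patients, with standard errors scaled to 91 per arm. The model fitted was logit P(event) = b0 + b1 × treatment + b2 × baseline urate.

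**3. Reading A: Week-2 responders only.** Odds ratio for febuxostat against allopurinol:

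| Week-2 response | g = 0.5 | g = 1 | g = 2 | Responders of 91 |
|---|---|---|---|---|
| 50/30% | 1.05 | 1.17 | 1.62 | 46 / 27 |
| 70/30% | 1.09 | 1.35 | 2.44 | 64 / 27 |
| 70/10% | 1.15 | 1.63 | 4.49 | 64 / 9 |
| 80/5% | 1.18 | 1.90 | 7.21 | 73 / 5 |

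With equal response (50/50%), or with g = 0, it is about 1.0 (0.98 to 1.01). Rejection at trial size is 5.3%, 8.0% and 20.7% across the 70/30% row. It is at most 14.7% at 70/10% and 11.5% at 80/5%, where so few patients remain in one arm (0.10 × 91 = 9.1; 0.05 × 91 = 4.6) that the estimate is unstable.

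The mechanism shows in the 70/30%, g = 1 case. Mean responsiveness among responders is 0.23 against 0.55, and 23.8% against 17.3% are later above target. The crude odds ratio is (0.238/0.762)/(0.173/0.827) = 1.49. Adjusting for baseline urate brings it to 1.35, not to 1.

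**4. Reading B: all FAS patients, non-reachers coded 0.** Only early responders can have the event. Ignoring baseline urate and with no responsiveness effect, the event rate is Week-2 response × 0.30:
- 50/30%: 0.15 against 0.09; odds ratio (0.15/0.85)/(0.09/0.91) = 1.8.
- 70/30%: 0.21 against 0.09; odds ratio (0.21/0.79)/(0.09/0.91) = 2.7.

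The fitted model, over g from 0 to 2, gives 1.9 to 2.7 and 3.1 to 5.9 respectively. Rejection at 70/30% is 63 to 66%. The difference arises without any selection on responsiveness.

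**5. The unconditional comparison.** Above target at the visit, in all FAS patients, gives odds ratios of 0.99 to 1.01 and 5.0% rejection in all 20 scenarios.

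**6. A sustained-control outcome.** For at target at Week 2 and at the later visit, the 70/30%, g = 1 case gives 0.70 × (1 − 0.238) = 53% against 0.30 × (1 − 0.173) = 25%, although late control is identical. This is a valid randomized outcome, but it measures early and late control together.

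**The case against.** The best defence has four parts.

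- **The SAP does not say that only responders are analysed.** This stands. A reader might infer a responder-only test from the wording of the item, but section 5.7.2 names the FAS and leaves the denominator open. Reading B does not rescue the test, however; it replaces selection bias with a difference in who can have the event.
- **The size is unknown.** This stands too. A reader might infer gross bias. A simulation on the urate scale, with a 40% mean Week-2 reduction on febuxostat, 15 to 30% on allopurinol and responsiveness SD 8 points, gives odds ratios from 2.3 to 20. The SAP supplies none of those inputs, and the value of 20 arises where about 2 of 91 allopurinol patients are Week-2 responders. It also does not say that either starting regimen is the less effective one.
- **A false significant result is not the likely outcome under Reading A.** Largely true. Rejection is at most about 21% in the table's scenarios. In 500 simulated trials of 91 per arm on the urate scale (visit noise SD 5 points assumed), it was 0 to 4% for allopurinol reductions of 20 to 30%, and 15% at a reduction of 15%. A biased and unstable estimate is the likelier harm. Under Reading B, rejection is high.
- **The unbiased comparison is already planned.** True: the item listed just before it is unconditional, and time to target is analysed in all patients. That limits the damage and makes the repair easy, but it does not justify testing the conditional item.

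**Conclusion.** Wrong as written. The item is tested between arms although it conditions on a response that treatment can affect, and its denominator is undefined. Neither available reading gives a randomized comparison of loss of control.

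With a true odds ratio of 1 for late control, Reading A gives no bias if the arms respond equally at Week 2 or responsiveness does not carry over. It gives 1.05 to 1.35 for response gaps of 20 to 40 points with g of 0.5 to 1, and about 7 at the extreme. The bias runs against the arm with more early responders. Reading B gives about 1.9 to 5.9 at 50/30% to 70/30%, and stays above 1 even without a responsiveness effect. All of these rest on the assumed Week-2 rates, the 30% late rate and the coefficient g. The documents support the mechanism, not any one of these values. Only this secondary item is affected; the primary analysis and the sample size are not.

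**What to change.** In section 5.7.2:
- Define the denominator of this item as patients at target at Week 2.
- Take the item out of the logistic regression list. Report it by arm as numbers and percentages at Weeks 12, 24 and 36, with the number at target at Week 2 beside each, and no between-arm test.
- State that between-arm inference on urate control rests on the FAS proportion at or below 6 mg/dl at Weeks 12, 24 and 36, which is already listed.
- Optionally add sustained control (at target at Week 2 and at the later visit) in all FAS patients, labelled as combined early and late control and not as loss of control.

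The secondary objective in section 2.2 can stay, since the item is still reported. If the protocol prescribes the test, section 3.2 should record the change before database lock. The cost is SAP wording, one table and the loss of the p-values for one secondary item. No new data are needed.

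### The additional three-class baseline sUA stratification of time to target has no class for a baseline of exactly 9.0 mg/dl (minor)

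*SAP*

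**What the plan says.** SAP section 5.7.2 plans time to the sUA target as follows: "Proportional hazards model with treatment group as covariate will be used to investigate". Three bullets come under it.

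- An unstratified analysis: "Time to achieve sUA target levels for all patients with baseline sUA as additional covariate".
- An analysis stratified by five baseline classes: "8.1-8.8 mg/dl, 8.9-9.6 mg/dl, 9.7-10.3 mg/dl, 10.4-11.0 mg/dl, >11 mg/dl". The same five classes appear among the secondary objectives in section 2.2.
- A further analysis, for all patients and by three coarser classes: ">8 and <9 mg/dl, >9 and <10 mg/dl, ≥ 10 mg/dl will additionally be presented". This version is not listed in section 2.2.

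The population for all of them is set at the start of section 5.7.2: "All secondary efficacy variables will be analyzed based on the FAS population". Section 4.2 defines that set as randomized patients with at least one dose and at least one PWV assessment after randomization. Nothing in it depends on baseline sUA.

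**The concern.** The three coarser classes should divide all baselines above 8 mg/dl between them. They do so at 10, where the upper class includes the boundary and the middle class excludes it. At 9 both neighbouring classes exclude the boundary, so a patient at exactly 9.0 has no class.

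A patient without a class cannot contribute to a comparison made within classes. Such a patient would be counted in the all-patients part of the bullet but missing from its stratified part, although both are meant to describe the same analysis set. The numbers by class would then fall short of the total, and the SAP gives no explanation for the difference.

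If the text stays as it is, the programmer must either leave these patients out or choose a class for them. That choice belongs in the plan, which section 3.1 says is finalized before database lock and unblinding.

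**Working it through.** The SAP states no figure on this point, so there is none to reproduce. The check has two parts: how the classes assign values, and how many patients could be affected.

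**Assignment.** Inputs: the two sets of classes in section 5.7.2. Each baseline from 8.1 to 13.0 mg/dl, in steps of 0.1, was placed in both sets exactly as written. Values around the two boundaries of the three-class set:

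| Baseline (mg/dl) | Above 8, below 9 | Above 9, below 10 | 10 or more | Five-class set |
|---|---|---|---|---|
| 8.9 | yes | no | no | 8.9-9.6 |
| 9.0 | no | no | no | 8.9-9.6 |
| 9.1 | no | yes | no | 8.9-9.6 |
| 9.9 | no | yes | no | 9.7-10.3 |
| 10.0 | no | no | yes | 9.7-10.3 |

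- Three-class set: 9.0 is the only value above 8 that matches no class. No value matches two. The result is the same in steps of 0.01.
- Five-class set: in steps of 0.1, every value from 8.1 upward matches exactly one class.
- Three-class set with the middle class changed to ≥9 and <10: every value from 8.1 to 13.0 matches exactly one class.

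**Number of patients.** Inputs from section 2.4: 182 patients to be randomized, and 2 × 79 = 158 planned after drop-out. Section 5.7.2 uses the full analysis set, whose size the SAP does not give. I take 158 to 182 as a working range for it.

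The SAP gives no baseline distribution and no reporting precision, so both are assumptions here. Baselines are taken as evenly spread over either 8.1-11.0 or 8.1-10.0 at one decimal, with the matching ranges at two decimals.

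Expected number at exactly 9 = number of patients ÷ number of possible values.

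One decimal:
- 8.1 to 11.0 has 30 values: 158 / 30 = 5.3 and 182 / 30 = 6.1.
- 8.1 to 10.0 has 20 values: 158 / 20 = 7.9 and 182 / 20 = 9.1.

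Two decimals:
- 8.01 to 11.00 has 300 values: 158 / 300 = 0.5 and 182 / 300 = 0.6.
- 8.01 to 10.00 has 200 values: 158 / 200 = 0.8 and 182 / 200 = 0.9.

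The expected loss is therefore about 5 to 9 patients at one decimal and fewer than 1 at two decimals. The class limits in the five-class set are written to 0.1 mg/dl, which suggests one decimal but does not establish it. The SAP also provides for baselines above 11. Patients there would lower these counts, because fewer would remain to be spread over the values near 9.

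**The case against.** The strongest reply is that little depends on this. The three-class version is an extra presentation of a secondary endpoint and is not among the objectives in section 2.2. The five-class version is listed there and handles 9.0 correctly. Patients at 9.0 also remain in the model with baseline sUA as a covariate and in the other sUA analyses. All of this stands, and it is why the point is minor. It does not remove the gap, because the SAP still plans an analysis whose rule cannot classify every patient it is meant to cover.

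An inequality sign may also have been lost at 9 when the text was extracted. That cannot be ruled out, but the inclusive sign at 10 survived on the same line, so it is not a likely explanation.

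A reader might infer three stronger points, which the SAP does not support.

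- **That these patients are lost from stratified time-to-target analysis altogether.** They are lost only from the three-class version.
- **That the five-class limits have gaps too.** With unrounded two-decimal values they would miss, for example, 8.81 to 8.89. But the limits are contiguous at the precision in which they are written, and the SAP nowhere says that sUA is delivered more finely. The two problems also pull in opposite directions: at one decimal the five classes have no gap, and at two decimals the gap at 9 nearly disappears.
- **That the two stratifications cannot be compared.** They differ in number of classes and in cut-points by design, and the SAP plans no class-by-class comparison.

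**Conclusion.** The point holds, for the additional three-class stratification only. As written, a baseline of exactly 9.0 mg/dl has no class, so patients with that value drop out of this supplementary analysis and its classes do not sum to the all-patients analysis beside it.

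The size ranges from under 1 patient to about 9. It depends on the assumed reporting precision, the assumed even spread and a full analysis set of 158 to 182. That the gap exists depends on none of these assumptions, since it can be read directly from the inequalities.

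The primary PWV analysis is not affected and the trial's main conclusion cannot change. Severity: minor.

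**What to change.** Before database lock, make one side of the boundary at 9 inclusive in SAP section 5.7.2. Writing the middle class as ≥9 and <10 mg/dl treats 9 as the same line already treats 10. The three classes then cover every baseline above 8 exactly once.

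The cost is one symbol in the SAP, plus the matching class definition in the program and the labels in its output. No other section has to change, because the three-class version appears only in section 5.7.2. The five classes, and their copy in section 2.2, can stay as they are at 0.1 mg/dl precision.
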